### 3.3. C. Research Design and Methods: R61 Phase.

**3.3. C.1. Overview.** The R61 Phase is designed to clarify engagement of the attention allocation target, to optimize dosage of GC-MRT (RCT comparing 8 vs. 12 sessions), and to explore whether the treatment engages two processes influencing attention allocation: disengagement from threat, and social reward.

**3.3. C.2. R61 Method: Patients:** The goal is to enroll a sample with clinically significant SAD, using few exclusion criteria to maximize generalizability. Patients will be obtained by clinical referral and recruitment notices posted online and locally. Forty adults age 18-60 with clinically significant SAD, as assessed by MINI structured interview and self-rated Liebowitz Social Anxiety Scale (LSAS-SR) total  $\geq 50$ , will enter the study after psychiatric clinical evaluation, including and Hamilton Rating Scale for Depression (HRSD). The LSAS cutoff score was chosen for optimal balance between diagnostic specificity and sensitivity for SAD. Key exclusion criteria will be at least moderately severe depression (HDRS 17-item score  $>20$ ), indicating greater need for non-experimental treatment; substance use disorder in the past 30 days (other than nicotine, or mild alcohol or cannabis abuse); bipolar or psychotic disorders; acute suicidal ideation (assessed by Columbia Suicide Severity Rating scale, CSSR); other unstable psychiatric, neurological, or medical conditions that could interfere with study participation or interpretation of outcomes; contraindication to MRI. (see Human Subjects for details).

[figure not shown]
The self-rated version of the LSAS will be used only at screening for eligibility assessment. The clinician-rated LSAS will be the primary outcome measure, assessed at baseline, during treatment, and post-treatment. Using the self-rated LSAS at screening avoids the bias that reportedly can occur when the primary outcome measure is the basis for an entry cutoff criterion, as raters could feel pressured to maximize baseline scores to meet the cutoff, thus distorting outcomes.

**3.3. C.3 R61 Intervention:** Patients will be randomized to 8 biweekly sessions of GC-MRT over 4 weeks vs. 12 sessions of GC-MRT over 8 weeks (8 biweekly, then 4 weekly), using GC-MRT as described above in the preliminary study, but without a control treatment – all R61 patients will receive active GC-MRT.

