### 3.3. C.4 Assessments :

These will include eye tracking of attention allocation during GC-MRT, self-ratings, clinician ratings (by an independent evaluator blind to GC-MRT dose assignment and scheduling of GC-MRT sessions), computer-based behavioral tasks, and MRI. Attention allocation will be assessed at every GC-MRT session. MRI assessments and behavioral tasks will be conducted pre- and post-treatment. All other outcome assessments will be conducted at baseline and at weeks 2, 4, and 8, and 3 months later (3-month follow-up).

**3.3. C.4.a. Primary Outcome Assessment for Target of Attention Allocation:** The primary outcome measure will be defined as % dwell time on threat faces (dwell time on threat faces/dwell time on all faces), derived from eye-tracking data obtained throughout each treatment session. Fixations will be defined as  $\geq 100$  ms of stable fixation within  $1^\circ$  visual angle. For each matrix we will define two Areas of Interest (AOI's), one of the eight disgust facial expressions (i.e., the threat AOI) and one of the eight neutral facial expressions (the neutral AOI). Attention allocation to threat will be measured by computing total dwell time in milliseconds per defined AOI and calculating the proportion of dwell time on the threat AOI relative to total dwell time on both AOI's, thus reflecting gaze allocation to threat stimuli. Percentage of dwell time on threat AOI across the 30 presented matrices for each session will be averaged for a final score of attention allocation to threat per session. As in the pilot study, to derive baseline % dwell time we will average the percentage of dwell time on threat AOI during the first five matrices presented in Session 1, as gaze-contingency learning has been shown to be minimal at this early stage.

**3.3. C.4.b. fMRI Tasks:** Patients will complete MRI twice (pre-treatment and post-treatment) using tasks that have been previously shown to differentiate SAD from control participants. Resting state data will be obtained for 15 minutes prior to task completion.

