### 3.3. C.5 Data Analysis and Hypothesis Testing

All quantitative measures will be graphed by group and checked for outliers and inconsistent values. If a variable has many outliers or shows heteroscedastic behavior (i.e., unequal variances), we shall consider transformations using a power function. Any remaining outliers will be winsorized (i.e., censored down to the nearest non-outlier value). Missing values. Missing values on outcome measures will be summarized by randomization group. We will test for differential missingness between groups. We will use mixed effect models for the statistical analyses, as these can analyze data with ignorable missingness (missing at random). G\*Power 3.1. and the R library longpower were used to calculate statistical power.

**R61.** Forty adults with SAD will be randomized to standard GC-MRT (8 sessions in 4 weeks) or extended GC-MRT (8 sessions in 12 weeks), with the target of attention allocation assessed at each session. **Aim 1:**

Hypothesis 1: *The target measure (% dwell time on threat faces) will decrease significantly during GC-MRT.*

The primary analysis will be intention-to-treat using a mixed effect model with change in % dwell time from baseline to the repeatedly measured outcome from all sessions after session 3 in both groups, using categorical time and baseline % dwell time as fixed effects, with an AR(1) correlation structure within subjects. The effect of interest will be the intercept, as this is a pooled analysis that does not differentiate between randomization groups or time points. A secondary analysis will use data from all sessions to test the categorical time effect predictor's effect, to identify time points with significant mean change scores adjusting for baseline medication use (yes/no). Additionally, the completer analysis will be a matched pair t-test of pre-post % dwell time values. Power Analysis: For the completer analysis, our already published data lead us to expect an effect size for reduction in the % dwell time of at least Cohen's  $d = 0.68$ . Assuming a 10% dropout with  $N=40$  enrolled subjects, and a 0.05 significance level, we will have at least 98% power to detect this change, with  $d = 0.48$  the minimum detectable effect size. For the repeated measures analysis, with within-subject autocorrelation parameter  $r = 0.6$ , we will have at least 80% power to detect an effect size of  $f = 0.17$ ,

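### The session-by-session secondary analysis of % dwell time loses half its patients after session 8, so its list of significant time points can make a constant effect look as if it fades

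*Combined protocol and SAP*

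**What the plan says.** Section 3.3. C.3 gives one arm "8 biweekly sessions of GC-MRT over 4 weeks" and the other "12 sessions of GC-MRT over 8 weeks (8 biweekly, then 4 weekly". The R61 Go-Nogo Criterion and the Human Subjects overview also refer to 8 or 12 sessions. Section 3.3. C.4 states: "Attention allocation will be assessed at every GC-MRT session".

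For Hypothesis 1, section 3.3. C.5 describes the primary model's effect of interest as the intercept, because "this is a pooled analysis that does not differentiate between randomization groups or time points". It then adds: "A secondary analysis will use data from all sessions to test the categorical time effect predictor's effect", the purpose being "to identify time points with significant mean change scores adjusting for baseline medication use". Medication use is the only adjustment named. No arm term is mentioned, and the analysis is not restricted to the sessions that both arms receive. The power analysis covers the pre-post completer test and the repeated-measures test, not single sessions.

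Section 3.3. C.5 also describes "extended GC-MRT (8 sessions in 12 weeks" weeks. Read literally, that would leave no sessions 9-12. The dose-selection rule uses both a 12-session/8-week and an 8-session/12-week label. These descriptions must be reconciled; this point rests on section 3.3. C.3.

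**The concern.** A list of significant and non-significant sessions is informative about time only if each session is tested with similar precision. Here the number of patients halves between session 8 and session 9, and those who remain all belong to one arm. Session spacing changes from twice weekly to weekly at the same point. A mixed model uses the available data properly, but it cannot restore the lost precision.

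R61 is meant to optimise dosage, so readers will look at sessions 9-12 to see whether target engagement holds. If the true change is constant, some late sessions may drop off the list only because fewer patients were measured, and the report could then describe an effect that fades once weekly sessions begin.

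**Working it through.** **Inputs.** 40 randomised; 20 per group enrolled and 18 per group completing (Aim 2 power paragraph); expected d = 0.68, alpha 0.05 and minimum detectable d = 0.48 (Hypothesis 1 power paragraph); AR(1) errors with r = 0.6 or 0.2 (same paragraph). Assumed: two-sided alpha, equal variance across sessions, and AR(1) on session number even though spacing changes after session 8.

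**1. The plan's own figure.** Paired t-test, noncentral t with n - 1 degrees of freedom and noncentrality d√n. With n = 36, power is 97.8% at d = 0.68 (stated: at least 98%), and the detectable d at 80% power is 0.480 (stated: 0.48). Both reproduce.

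**2. The same test at one late session.** With n = 18, power is 77.6% at d = 0.68 and the detectable d is 0.70. This ignores what the model borrows from earlier sessions, so it is a lower bound for power.

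**3. Standard errors under the plan's AR(1) model.** In SD units, the session 8 mean has variance 1/36, so SE = 0.1667. For session 8 + k, observed in 18 patients, the variance is (1 - r^(2k))/18 + r^(2k)/36.

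| | r = 0.6 | r = 0.2 |
|---|---|---|
| Session 9 (k = 1) | √(0.64/18 + 0.36/36) = 0.2134; ratio to session 8 1.28 | √(0.96/18 + 0.04/36) = 0.2333; ratio 1.40 |
| Session 12 (k = 4) | 0.2347; ratio 1.41 | 0.2357; ratio 1.41 |

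Borrowing helps mainly at session 9 and is almost gone by session 12.

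**4. Power at a constant d = 0.68** (normal approximation, Φ(d/SE - 1.96)).
- Session 8: 0.68/0.1667 = 4.08, power 98%.
- Session 9: 0.68/0.2134 = 3.19, power 89% (r = 0.6); 0.68/0.2333 = 2.91, power 83% (r = 0.2).
- Session 12: 83% (r = 0.6) and 82% (r = 0.2).

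Across the wider set of correlation assumptions simulated, the range for sessions 9-12 is about 82-92%. The higher values belong to stronger or more persistent within-patient correlation, which allows more borrowing.

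**5. How often a constant effect looks as if it fades.** The categorical-time AR(1) model was simulated with 18 completers per arm and a constant effect. The entries are the chance that at least one of sessions 9-12 is non-significant, given a significant session 8.

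| True constant d | Coverage as planned | All 36 measured at every session |
|---|---|---|
| 0.68 | 27-52% | 3-8% |
| 0.48 | 62-88% | 28-51% |

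At the expected effect, nearly all of the pattern comes from coverage. At d = 0.48, a large part is ordinary repeated testing at about 80% power.

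**6. Precision of a late contrast, r = 0.6.** Take the mean of sessions 9-12 minus session 8. The mean of sessions 9-12 has variance 0.592 per patient and covariance 0.3264 with session 8.
- Within extended-arm patients: √((1 + 0.592 - 2 × 0.3264)/18) = 0.23.
- Pooled model: √((0.592 - 0.3264²)/18 + (1 - 0.3264)²/36) = 0.20.

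**The case against.** The best defence has four parts, and most of it stands.

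- **Significance does not fall by construction.** A reader might infer that late sessions are bound to turn non-significant. They are not. At d = 0.68 each late session keeps about 82-92% model-based power, and in most simulated trials the pattern did not appear at the AR(1) values the plan uses, or was close to even at the lower one. A growing effect can also offset the loss: a rise of about 41% (0.68 × 1.41 ≈ 0.96) keeps the same expected test statistic.
- **The session means are not biased by design.** A reader might infer that pooling turns an arm difference into a time trend. An assumed constant arm difference of 0.3 SD would shift the late average by 0.15 × (1 - 0.3264) ≈ 0.10 SD at r = 0.6. But the arms are randomised and, under section 3.3. C.3, follow the same schedule through session 8, so only a chance difference could exist before session 9. Aim 2 expects no group difference in % dwell time at the last session. The pooled late contrast also keeps type I error at or below about 5%.
- **The secondary model is not fully specified.** The statement that groups are not differentiated describes the primary analysis. The absence of an arm term in the secondary model is therefore an inference from silence.
- **No decision uses this analysis.** Go/no-go uses last-session % dwell time for each treatment. If both doses pass, the dose rule uses the LSAS difference at 8 weeks.

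What remains is that the stated purpose is to sort sessions by significance on one scale, when the number contributing halves part-way along it. Graphing measures by group and comparing groups at the last session do not correct that list.

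**Conclusion.** The point holds as a minor improvement to a secondary analysis. It is precision and power that fall after session 8 by construction. At the plan's expected effect this raises the chance of an apparent fade from 3-8% to about 27-52%. The documents do not support a claim of biased session means or of a threatened go/no-go or dose decision. The figures assume the 12-session extended arm of section 3.3. C.3, 18 completers per arm, a constant true effect, two-sided 5% tests and equal variance across sessions. If the extended arm had only 8 sessions, as one sentence in section 3.3. C.5 reads, the point would not arise.

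**What to change.** In the Hypothesis 1 secondary analysis:

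1. Limit the pooled session-by-session significance test to sessions 1-8.
2. Report sessions 9-12 as extended-arm estimates with confidence intervals, and give the number of patients contributing at every session.
3. Describe late change by a within-patient contrast, the mean of sessions 9-12 minus the same patients' session 8, with a confidence interval. Do not use significant/non-significant labels for it.
4. Reconcile the descriptions of the extended arm in sections 3.3. C.3 and 3.3. C.5 and in the dose-selection rule.

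This is a change of wording only and needs no new data. It does not recover precision, since sessions 9-12 still rest on about 18 patients. When the arms do not differ, the within-patient contrast is somewhat less precise than the pooled model contrast (SD 0.23 against 0.20 at AR(1) 0.6). Under pure AR(1), that lowers power for a 0.4 SD late gain from 52% to 39%. With stable differences between patients, its power was slightly higher in simulation (55% against 51%, and 63% against 58%).

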corresponding to  $d = 0.34$ , while with  $r = 0.2$ , the minimal detectable effect size is  $f = 0.23$  or  $d = 0.45$ . In either case, the power for  $d = 0.68$  will be  $>99\%$ .

**Aim 2: Hypothesis 2:** *Eight weeks after starting treatment, mean Liebowitz Social Anxiety Scale (LSAS) total score will be significantly lower in the 8-week treatment group than in the 4-week group.* We will use a t-test for the change score at 8 weeks after starting treatment for completers. We will also compare groups on % dwell time at last session but do not expect a group difference. Power Analysis. We do not have preliminary data for the 8-week dose of treatment. For the two-group t-test, with  $n=20$  per group enrolled, and 18 per group completers (10% dropout), we will have 80% power to detect an effect of size  $d=0.96$  or larger. Thus we will be able to detect large effect sizes for the dosage difference. However, dose selection for the R33 will not require statistically significant superiority (see criterion for selecting dose, below).

**Aim 3 (Exploratory):** (See below for processing MRI and tasks data) We will test the association between change in attention control and reward processing and change in % dwell time by Pearson correlation coefficients. *We will also explore predictors of target engagement (baseline attention allocation and neural activation), to advance personalized treatment.* We will fit mixed effect regression models as described in Hyp 1, with repeatedly measured reduction in % dwell time as outcomes, with the predictors listed above.

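### The repeated-measures power statement for Hypothesis 1 does not fit the named intercept test: its detectable effect falls as within-subject correlation rises, when it should rise

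*Combined protocol and SAP*

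**What the plan says.** All of this is in section 3.3. C.5, R61, Aim 1, unless noted.

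- **Outcome of the primary model:** "change in % dwell time from baseline to the repeatedly measured outcome from all sessions after session 3 in both groups". The correlation structure is given separately as "with an AR(1) correlation structure within subjects"; the fixed effects are time, as a category, and baseline % dwell time.
- **Effect tested:** "The effect of interest will be the intercept, as this is a pooled analysis that does not differentiate between randomization groups or time points". The test of the categorical time effect belongs to a separate, secondary analysis.
- **Sessions by arm (section 3.3. C.3):** "Patients will be randomized to 8 biweekly sessions of GC-MRT over 4 weeks vs. 12 sessions of GC-MRT over 8 weeks". Sessions after the third therefore number 5 in one arm and 9 in the other.
- **Completer power (matched-pair t-test):** the inputs are 40 enrolled, 10% dropout and alpha 0.05. The result for the expected d = 0.68 is "we will have at least 98% power to detect this change, with $d = 0.48$ the minimum detectable effect size".
- **Repeated-measures power:** the sentence that opens "For the repeated measures analysis, with within-subject autocorrelation parameter" puts power at 80% or more for f = 0.17, given as d = 0.34, when r = 0.6. The values for r = 0.2 are f = 0.23 and d = 0.45, introduced by the words "the minimal detectable effect size is". Power for d = 0.68 is put above 99% at both correlations.

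G*Power 3.1 and the R library longpower are named as software. The procedure used, the number of measurements, and the scale on which r and d are defined are not given.

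**The concern.** The intercept test asks whether the average change from baseline differs from zero. Averaging several sessions per patient helps most when those sessions carry separate information, that is, when r is low. At r near 1 the extra sessions add nothing and the test falls back to a single change score per patient. The detectable effect must therefore grow with r, yet the plan has it shrinking from 0.45 to 0.34 as r goes from 0.2 to 0.6.

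This is the only sensitivity stated for the primary R61 analysis of target engagement. As written, it presents the less favourable correlation as the more favourable one. It also sets its d values beside d = 0.68 and d = 0.48 without showing that all four are in the same units.

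**Working it through.** **Inputs.** 40 enrolled less 10% gives n = 36. Alpha is 0.05, taken as two-sided because that reproduces the completer figures. Sessions after session 3: m = 5 (8-session arm) and m = 9 (12-session arm), 18 patients each. r = 0.2 and 0.6.

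**1. Completer figures.** A one-sample (paired) noncentral t at n = 36 gives 97.8% power for d = 0.68 and a minimum detectable d of 0.480. Both agree with the plan, so d = 0.68 and d = 0.48 are in SDs of the change score.

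**2. The stated f values.** For a within-subject factor, λ = f²·n·m/(1 − r), with m − 1 and (n − 1)(m − 1) degrees of freedom. With n = 36 and m = 5 (4 and 140 df), 80% power needs:

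- r = 0.6: f = 0.166 (stated 0.17)
- r = 0.2: f = 0.234 (stated 0.23)

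Over m = 2 to 12 with n = 36 or 40, no other combination matches both; the nearest is n = 40, m = 4, with 0.168 and 0.237. This F test compares sessions with one another. Its effect is zero if dwell time has dropped by session 4 and then stays flat.

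The d values do not follow from it. Doubling gives 2 × 0.166 = 0.33 and 2 × 0.234 = 0.47, against the stated 0.34 and 0.45. Doubling the rounded 0.23 gives 0.46. In any case d = 2f holds for a two-level factor and does not turn a five-level f into a mean change from baseline.

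**3. The intercept test.** Detectable d = 0.480 × √V, where V is the variance of a patient's session mean relative to that of one change score.

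*AR(1), simple session means:* V = [m + 2Σ(m − k)r^k]/m², k = 1 to m − 1.

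*AR(1), generalised least squares:* V = (1 + r)/[m − (m − 2)r].

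*Constant correlation:* V = [1 + (m − 1)r]/m.

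| Structure | r | V, m = 5 | V, m = 9 | V, arms combined | Detectable d | Stated d |
|---|---|---|---|---|---|---|
| AR(1), simple means | 0.2 | 0.275 | 0.159 | 0.217 | 0.22 | 0.45 |
| AR(1), simple means | 0.6 | 0.523 | 0.353 | 0.438 | 0.32 | 0.34 |
| AR(1), GLS | 0.2 | 0.273 | 0.158 | 0.200 | 0.21 | 0.45 |
| AR(1), GLS | 0.6 | 0.500 | 0.333 | 0.400 | 0.30 | 0.34 |
| Constant | 0.2 | 0.360 | 0.289 | 0.324 | 0.27 | 0.45 |
| Constant | 0.6 | 0.680 | 0.644 | 0.662 | 0.39 | 0.34 |

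For simple means and constant correlation the arms are combined by averaging V over equal numbers of patients. For GLS they are combined by precision; for example, at r = 0.6, 2/(1/0.500 + 1/0.333) = 0.400. In every structure the detectable effect rises with r.

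**4. Power at the plan's own effects.** Under AR(1) with 5 and 9 sessions, power for d = 0.34 at r = 0.6 is 85 to 88%. Power for d = 0.45 at r = 0.2 is at least 99.9%. For d = 0.68 the lowest value found is 99.8% (constant correlation, r = 0.6).

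**The case against.** The strongest defence is that r may not be the correlation among change scores. Suppose it is a constant correlation among raw scores, baseline included, and the test is mean post-baseline score minus baseline. Then V = 1 + [1 + (m − 1)r]/m − 2r. Averaged over 5 and 9 sessions this gives d = 0.33 at r = 0.6 and 0.46 at r = 0.2: the plan's direction, within about 0.01 of its figures. This stands as a possible origin, but it does not rescue the text. It is not AR(1) on change scores, it does not match exactly, and its d is in raw-score SDs, so it could not be set beside d = 0.68 and d = 0.48 as the plan does.

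A reader might also infer, as fact, that the sponsor powered a test of a different null hypothesis. The documents do not support that. They name no procedure, and only the rounded f values match. In the F test the ratio of detectable effects is √(0.8/0.4) = 1.41 for any n and m with d = 2f. The stated d ratio is 0.45/0.34 = 1.32, and rounding allows only 1.29 (0.445/0.345) to 1.36 (0.455/0.335).

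Nor can one infer that the study is underpowered. Under the plan's AR(1) model both stated d values exceed what is needed. The Go-Nogo criterion uses the decrease at the last session, not these figures.

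**Conclusion.** The concern holds as a mismatch between the power statement and the named primary test. With r read as the plan's AR(1) correlation of change scores, the direction is reversed, and at r = 0.2 the stated 0.45 is about twice the detectable effect (0.45/0.22 = 2.0). At r = 0.6 the stated 0.34 is slightly larger than the 0.30 to 0.32 required. Where the figures came from remains an inference.

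The practical effect is small: the >99% power for d = 0.68 holds throughout and N = 40 is unaffected. The one unfavourable case is constant correlation at r = 0.6, where the detectable effect is 0.39 rather than 0.34; the plan does not specify that structure.

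Assumptions: the intercept is read as the pooled mean change, as the plan describes it; 36 patients contribute all planned sessions; and d is in SDs of the change score. The model adjusts for baseline, so the residual SD could differ, and the documents give no figure for it. The count of 9 sessions rests on section 3.3. C.3. Section 3.3. C.5 describes the extended arm as 8 sessions in 12 weeks, and the two must be reconciled. With 5 sessions in both arms, AR(1) gives 0.25 and 0.34 to 0.35, so the direction is unchanged and the stated 0.34 is then about right rather than conservative.

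**What to change.** Replace the two repeated-measures power sentences with the 80%-power detectable mean change for the intercept test, in change-score SDs, at n = 36 and two-sided 0.05, with 5 sessions in the 8-session arm and 9 in the 12-session arm:

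- AR(1): about d = 0.22 at r = 0.2 and 0.30 to 0.32 at r = 0.6.
- Constant correlation, as a sensitivity case: about 0.27 and 0.39.

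State the number of sessions per arm, the procedure, and the scale of r and d. Say that higher correlation is the less favourable case. Delete the f values and their conversion to d. Keep the statement on d = 0.68.

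The cost is a wording change only, with no change to sample size, design or analysis. The small downside is having to report a sensitivity figure (0.39) less favourable than the stated 0.34.

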**R61 Go-Nogo Criterion:** Mean % dwell time on threat faces during the last session of the 8-session or 12-session treatment will decrease by more than 7.2 percentage points relative to baseline, corresponding to a medium effect size of Cohen's  $d=0.48$ , based on preliminary data. We have  $>80\%$  power to detect this difference under all scenarios. Clinical significance of cutoff: Based on preliminary data, since % dwell time reduction will partially mediate clinical symptom reduction, this effect corresponds to symptom reduction of  $d = 1.34$ , corresponding to 21.3 points on the LSAS scale. **R61 criterion for selecting dose for the R33:** If only one dosage group passes the Go-Nogo Criterion, that dose will be selected for the R33. If both dosage groups satisfy the Go-Nogo Criterion, we will decide based on the following: If improvement (decrease) in LSAS total score 8 weeks after starting treatment is at least 7 points greater in the 12-session/8-week treatment group than in the 8-session/ 4-week treatment group, we will use the 8-session/12-week treatment in the R33.

**Aim 4: Hypothesis 3:** *Compared to control treatment, GC-MRT will significantly improve symptoms (LSAS) & QoL (Quality of Life Enjoyment & Satisfaction Scale, QLESQ: a) at post-treatment and b) at 3-month follow-up.* As primary analysis, we will use a two-sample t-test for the LSAS change scores at the last session in completer subjects. For the 3-month follow-up, a similar analysis will be performed. Secondary analysis will be similar analyses of the QLESQ, and a mixed effects model of each outcome with change score (relative to baseline) as the outcome, and randomization group, time point, and the baseline score as the predictors. Power Analysis. We assume 10% drop-out in each group. From our preliminary data analysis, expected effect size for reduction in LSAS for completer subjects, compared to controls, will be  $d = 1.35$ . Using a two-sample t-test, with Bonferroni-corrected 0.025 significance level, we will have 99% power to detect this. We do not have preliminary data for the QLESQ; the minimal detectable effect size for the change difference will be  $d=0.74$ , a moderate effect size.

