## PROTECTION OF HUMAN SUBJECTS

### a. Human Subjects Involvement, Characteristics, and Design

#### **Overview:**

We anticipate recruiting and entering 40 adults, age 18-60, with social anxiety disorder. They will complete diagnostic evaluations and begin full testing, including procedures of behavioral tasks, MRI, and 8 or 12 sessions of computer-based treatment. We estimate that overall 10% of participants will not complete all procedures due to noncompliance or movement artifacts.

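### Aim 2 tests LSAS only by an unadjusted completer t-test, and Aim 4 makes the same kind of test primary, although the plan adopts mixed models for missing data

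*Combined protocol and SAP*

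**What the plan says.** Section 3.3. C.5, Aim 2 / Hypothesis 2, compares the two dosage groups on LSAS. Its only LSAS analysis is: "We will use a t-test for the change score at 8 weeks after starting treatment for completers". The power paragraph starts from 20 enrolled per group and arrives at "18 per group completers (10% dropout"). It adds that "dose selection for the R33 will not require statistically significant superiority".

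For Aim 4 / Hypothesis 3 the primary analysis is stated as "we will use a two-sample t-test for the LSAS change scores at the last session in completer subjects". A mixed model with arm, time point and baseline score is listed as secondary.

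The opening paragraph of the same section takes a different line on missing data: "We will use mixed effect models for the statistical analyses, as these can analyze data with ignorable missingness (missing at random"). It also says: "We will test for differential missingness between groups". For Aim 1 (% dwell time): "The primary analysis will be intention-to-treat using a mixed effect model", adjusted for baseline, with the completer t-test as an additional analysis.

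Three other places bear on the point:
- LSAS is rated at weeks 0, 2, 4 and 8 and at 3 months (sections 3.3. C.4 and C.4.d), and randomisation is stratified by baseline medication use (C.4.d).
- No definition of a completer is given. The nearest text, in the Overview under Protection of Human Subjects, is: "We estimate that overall 10% of participants will not complete all procedures due to noncompliance or movement artifacts".
- If both doses pass the Go-Nogo criterion, the R33 dose depends on whether the gap in LSAS improvement at week 8 is at least 7 points. That rule names no analysis set or estimator.

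**The concern.** Patients who complete are selected after randomisation, so comparing them does not fully preserve the randomised comparison. The two R61 arms differ in length (4 or 8 weeks of sessions). A completer defined by attendance would therefore have to stay in treatment twice as long in one arm as in the other. If completion means every procedure including a usable scan, patients with a valid week-8 LSAS could be left out.

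The t-test also leaves collected information unused: baseline LSAS as a covariate, the week-2 and week-4 scores, and the stratum used in randomisation.

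The stake is mainly the LSAS dose contrast. The Aim 2 significance test does not choose the dose, but the same contrast enters the 7-point comparison. With population and estimator left open, the answer could depend on a choice made after the data are seen.

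**Working it through.** **1. The plan's own figures.** Noncentral t, two-sided. Aim 2 states no alpha; 0.05 is assumed and reproduces the plan.
- Aim 2, 18 per group: power at d = 0.96 is 79.9%, detectable d is 0.961. The plan's 0.96 is confirmed.
- Aim 4, 36 per group (80 enrolled less 10%, equal arms assumed), alpha 0.025: detectable d is 0.740, matching the plan; power at d = 1.35 is 99.96% (plan: 99%).

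The power arithmetic is sound. The issue is the method and the analysis set.

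**2. Gain from baseline adjustment.** Let rho be the correlation of baseline with week-8 LSAS and k the ratio of baseline SD to week-8 SD. Then

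variance(adjusted) / variance(raw change) = (1 − rho²) / (1 + k² − 2·rho·k).

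For example, with rho = 0.4 and k = 1, 0.84 / 1.20 = 0.70. Neither quantity is in the documents, so a range is assumed. The LSAS-SR entry cutoff may push k below 1. With 18 per group and 32 df:

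| k | rho | variance ratio | detectable d | power at d = 0.96 |
|---|---|---|---|---|
| 1 | 0.4 | 0.700 | 0.81 | 92% |
| 1 | 0.7 | 0.850 | 0.89 | 86% |
| 0.8 | 0.4 | 0.840 | 0.88 | 86% |
| 0.8 | 0.7 | 0.981 | 0.95 | 81% |
| 0.7 | 0.4 | 0.903 | 0.92 | 84% |
| 0.7 | 0.7 | 1.000 | 0.96 | 80% |

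Separately, if the 10% counted as non-completers do have a week-8 LSAS, counting 20 per group moves the unadjusted detectable d from 0.96 to 0.91.

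**3. The 7-point comparison.** The Go-Nogo paragraph equates d = 1.34 with 21.3 LSAS points, so SD = 21.3 / 1.34 = 15.9 (assumed to apply to change scores). With 18 per group, SE = 15.9 × √(2/18) = 5.30. If the doses do not differ, P(gap ≥ 7) = 1 − Φ(7 / 5.30) = 9.3%. After adjustment it is 5.7–7.6% (k = 1), 7.5–9.1% (k = 0.8) or 8.2–9.3% (k = 0.7).

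**4. Can the planned missingness test cover this?** With 20 per arm, 2 against 4 dropouts gives Fisher p = 0.66. Power is 7.2% for 10% against 20% dropout, and 24% for 10% against 30%.

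**5. Completer bias, by assumption only.** Simulated R61 trials: 20 per arm, weeks 0/2/4/8, change SD 15.9, rho 0.4–0.7, k 0.7–1, post-baseline correlation 0.75. The model was fitted by maximum likelihood with unstructured covariance and without the stratum. All inputs except N, visits and 10% dropout are assumptions. Bias in LSAS points:

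| Dropout | Completer t-test | Mixed model |
|---|---|---|
| Random, 10% | none | none |
| Response-driven, alike in both arms | at most 0.2 | at most 0.2 |
| Poor week-4 responders leave one arm, 10% | 0.8–1.2 | within 0.1 |
| Same, 20% | 1.5–2.3 | within 0.1 |
| One arm, driven by the unseen week-8 change, 10% | 1.4–1.6 | 0.4–1.0 |
| Same, 20% | 2.8–3.2 | 0.7–2.2 |

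With random 10% dropout the empirical SE was 5.25–5.38 for completers and 4.28–5.32 for the model.

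**The case against.** **The general mixed-model sentence already covers LSAS.** It heads the analysis section for all aims, so this could be called a gap between a general commitment and Aim 2. That is fair as far as it goes. But the sentence specifies no LSAS model for Aim 2, and the specific text names a t-test in completers. Someone following the plan would run the t-test.

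**The harm is small or unknown.** The plan expects 10% dropout in each group, and if dropout is alike in both arms the bias is about zero. The larger biases need response-driven dropout in one arm, which nothing in the documents predicts. The precision gain vanishes at rho = k = 0.7. All of this stands, and it limits the severity.

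**The completer ambiguity is inferred.** The Overview sentence estimates completion of procedures and does not define the LSAS analysis set; the Aim 2 wording reads naturally as patients who did not drop out. This stands too, so the move from 0.96 to 0.91 is conditional. By itself the missing definition would be a wording point.

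**Aim 4 is a matter of ranking.** A baseline-adjusted model is already prespecified there and LSAS power is not in question. No separate R33 design section was available, so the remark rests on the Aim 4 text and the randomisation paragraph. The argument for Aim 4 is only that every patient with data should count in the primary analysis.

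**Conclusion.** The concern holds and should be fixed; it does not invalidate the trial. Aim 2 has no specified all-randomised or baseline-adjusted LSAS analysis, and Aim 4 puts a completer t-test above its better model. Both sit uneasily with the plan's own missing-data reasoning and with Aim 1.

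The change would cut the variance of the Aim 2 contrast by between 0 and 30%, for assumed rho 0.4–0.7 and k 0.7–1. It would also reduce a possible completer bias that is modest against an SE of 5.3 points and cannot be estimated from the documents. Neither figure is the whole case: the model uses data already planned, and it closes an open choice of estimator in the 7-point comparison. Confidence is high on what the text says and on the closed-form figures. The bias figures are illustrative, do not cover Aim 4, and come from a model without the stratum.

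**What to change.** **Aim 2.** Make primary a mixed model in all randomised patients, using baseline and every available LSAS up to week 8, with visit, arm-by-visit and medication stratum. Use a small-sample correction such as Kenward-Roger and name a simpler covariance as fallback. Test the week-8 arm contrast. State that the 7-point comparison uses this estimate, with the threshold unchanged.

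**Aim 4.** Promote the planned mixed model to primary, add arm-by-visit and medication stratum, and include every patient with LSAS data whether or not treatment or MRI was completed.

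**Both aims.** Define a completer and keep the completer t-tests as sensitivity analyses. A delta-adjusted analysis for data missing not at random is a useful option.

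**Cost.** Wording in the analysis plan, settled before outcome data are seen; no extra patients or R61 LSAS visits. The model spends a few degrees of freedom and relies on the missing-at-random assumption the plan already makes. It reduces but does not remove bias if dropout depends on the unseen week-8 score, and patients with only a baseline value add nothing to the arm contrast. Four visits with unstructured covariance mean 4 × 5 / 2 = 10 covariance parameters from 40 patients. Hence the correction: without it a nominal 5% Wald test with 32 df runs at about 5.9% (REML) to 7.4% (ML).
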